7.2.2 Statistical Analysis Methods for Primary Outcome

Because the most intensive intervention period is during the initial 3-4 months, the primary outcome is measured at 180 days (6 months) to capture the main intervention effect. Given the primary outcome is the number of days of risky opioid use within the first 180 days following the baseline assessment collected with HLM, a mixed effects negative binomial model with a log link will be fit to estimate the difference in means between treatment and control groups. Fixed effects include treatment effect, site effect, and the baseline value of the response variable (days of use within 30 days prior to the baseline assessment timepoint), which may improve precision. Random PCP intercepts are to account for within-PCP correlation of participant response values. Since randomization was at PCP team level where PCPs practiced in teams and shared patients regularly, PCP cluster was specified as PCP/PCP team which was the unit of randomization, that is, if two or more PCPs are randomized as a single cluster, they will be analyzed as a single cluster. Letting Y_{jk} denote the response variable of a participant in site j with PCP k , treatment denotes a binary treatment indicator variable, site denotes a multi-level categorical variable representing study sites, and baseline denote the baseline value, the formula for the log-transformed expectation of Y_{jk} is given:

$$\log[E(Y_{jk})] = \beta_0 + \beta_1 \cdot \text{treatment} + \beta_2 \cdot \text{baseline} + \beta_3 \cdot \text{site} + \gamma_k,$$

where γ_k is normally distributed with mean zero and standard deviation σ_γ representing random effect by within-PCP correlation of participant responses. The negative binomial model allows for potential overdispersion of the response variable, so is more flexible than a Poisson distribution which would require the mean to be equal to the variance.

The primary hypothesis will be evaluated by testing whether the treatment effect, β_1 , is different from zero. This is equivalent to testing whether the control mean is different from the intervention mean.

The template SAS code for the primary analysis is:

```
PROC GLIMMIX DATA=dat METHOD=quad;
  CLASS PCP treat site;
  MODEL daysin180 = treat site baseline / solution DIST=negbin LINK=log ddfm=bw;
  RANDOM intercept / SUBJECT= PCP;
RUN;
```

Where:

“dat” is the name of the dataset with one row per patient participant,

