 - It is assumed that patient participants who drop out will have higher use after their dropout date than those who remain in the study, that is, that days of use after the withdrawal timepoint for dropouts in the treatment arm may more closely resemble that of controls than that of other treated patient participants. The values of missingness due to dropout might not retain the trend of prior observations since they are not exposed in the study environment due to various reasons, therefore the mechanism of missingness is assumed missing not at random (MNAR).

For the imputation of the primary outcome, two separate imputation procedures will be used to complete the imputation process for intermittent missingness and dropout. In the first step, the MI procedure statement uses the Markov Chain Monte Carlo (MCMC) method to impute the values of missing outcomes from intermittent missingness under the missing assumption of MAR. The variables specified in the mixed-effect regression model in Section 7.2.2, are included for imputation of primary outcome. The SAS code for imputing missing data from intermittent missingness is given below.

```
/* imputing the intermittent missingness with MAR assumption */
PROC MI DATA=datamiss nimpute=30 OUT=outimp1 SEED = 100623
min=. . 0 0 0 0 0 0
max=. . 30 30 30 30 30 30;
by treat;
mcmc impute=monotone;
VAR treat site baseline daysinmon1-daysinmon6;
RUN;
```

In this step, this MI procedure produces 30 imputed datasets by filling in the missing values from intermittent missingness with statement “impute=monotone”, and then produces the datasets as monotone missingness. The missing values due to intermittent missingness are imputed assuming that the intervention effect is still carried out while they remain enrolled in the study.

Next, MI procedure is to impute missing values from the dropouts under assumption of missing not at random (MNAR), which is a control-based pattern imputation assuming that after dropout, the unobserved values in the intervention group follow the path of observed values in control group. Based on this assumption, only the observed values in EUC group are used to derive the posterior distribution of the parameters from which the missing values in both EUC and STOP group are imputed. This approach is conservative as it tends to reduce the difference between STOP group and EUC group. The SAS code for imputing missing data from dropout is given below.

```

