/* imputing the dropouts with MNAR assumption */
PROC MI DATA=outimp1 nimpute=1 OUT=outimp2 SEED = 100623
min=. . 0 0 0 0 0 0
max=. . 30 30 30 30 30 30;
CLASS treat site;
VAR treat site baseline daysinmon1-daysinmon6;
monotone REG;
MNAR model(daysinmon1-daysinmon6/ modelobs=(treat="0"));
RUN;
```

As the 30 completed datasets are generated, analyses of the 30 imputed datasets using the standard procedure for the mixed effects negative binomial model are performed separately for each imputed dataset using “by _imputation” statement.

```
/* analysis model */
PROC GLIMMIX DATA = outmi NOCLPRINT;
BY _imputation_;
CLASS PCP treat site;
MODEL daysin180 = treat site baseline / DIST=negbin LINK=log;
RANDOM intercept / SUBJECT = PCP;
LSMEANS treat / pdiff ILINK;
ODS OUTPUT PARAMETERESTIMATES=GPARMS;
RUN;
```

To draw statistical inference based on the results from the 30 imputations, the combination rules are applied in MIANALYZE procedure [7, 8]. Proc MIANALYZE is set to estimate the pooled variance from two components: within-imputation variance and between-imputation variance. Within-imputation variance is the average of the mean of the within variance estimate in each imputed dataset. Between-imputation variance reflects the extra variance due to the missing data, which is estimated by taking the variance of parameter of interest estimated over imputed datasets. Simulations indicate that the 30 imputations will produce enough efficiency to avoid diminishing power for detection of the treatment effect [9].

```
/* pooling the individual estimates from each imputed datasets into one set of estimates*/
PROC MIANALYZE PARMS=mixparms;
CLASS visno;
MODELEFFECTS intercept treat site baseline;
RUN;
```

Statistical inferences of the treatment effect will be presented as the rate ratio along with its 95% confidence interval adjusting for site effect and the values of risky opioid use within 30 days prior to the baseline assessment based on the combination of the 30 imputed datasets.

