9.0 SIGNIFICANCE TESTING AND MULTIPLICITY

The primary outcome will be evaluated using a two-sided test with a type I error rate of 5%. There are several secondary outcomes; however, adjustments for multiple comparisons will not be performed since these are not part of the study's primary objective. The resulting p values will be interpreted appropriately in the context of the multiple tests being performed. Effect estimates will be presented with confidence intervals, and interpretation of hypothesis tests for multiple secondary outcomes will take into consideration the number of tests that were performed. Reporting of results will be transparent, with null as well as significant findings reported.

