10.2 Table 6: Power Estimates Based on 1000 Simulations

Condi- tion	No. of PCPs	No. of pts per PCP	Scenario	Group means (3-mo, 6-mo)		Power
				Control	Treatment	
A	60	8	1: Constant effect, no assessment impact	20, 20	14, 14	0.98
			2: Waning effect, no assessment impact	20, 20	14, 15	0.95
			3: Constant effect, assessment impact	19, 18	13, 12	0.99
			4: Waning effect, assessment impact	19, 18	13, 13	0.97
B	60	4	1: Constant effect, no assessment impact	20, 20	14, 14	0.97
			2: Waning effect, no assessment impact	20, 20	14, 15	0.93
			3: Constant effect, assessment impact	19, 18	13, 12	0.97
			4: Waning effect, assessment impact	19, 18	13, 13	0.95
C	60	5	1: Constant effect, no assessment impact	20, 20	14, 14	0.97
			2: Waning effect, no assessment impact	20, 20	14, 15	0.93
			3: Constant effect, assessment impact	19, 18	13, 12	0.99
			4: Waning effect, assessment impact	19, 18	13, 13	0.97
D	50	4	1: Constant effect, no assessment impact	20, 20	14, 14	0.93
			2: Waning effect, no assessment impact	20, 20	14, 15	0.89
			3: Constant effect, assessment impact	19, 18	13, 12	0.94
			4: Waning effect, assessment impact	19, 18	13, 13	0.91

Note: All simulations assume 20% dropout.

Within the anticipated range of mean values (10-20 days per 90), power increases as the control group mean decreases. Therefore, power would be even higher if the control group mean is 10 or 15 instead of 20, as long as the additive decrease remains the same (-6 days per 90). Additionally, power will be higher if the additive decrease is higher than planned.

Effect of Reducing Number of PCPs and patient participants per PCP: All scenarios and conditions presented have power in the range of 89% - 99%, allowing us to conclude that 1) reducing number of patient participants for each of 60 PCPs has minimal impact to power; and 2) even if 50 PCPs enrolled 4 participants each for a total of 200 participants, power is still in the acceptable range across all scenarios of time trends of the intervention effect and assessment impact in the control group.

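### SAP 7.2.3 prints an imputation and pooling procedure that matches neither its own text nor the 7.2.2 model: the pooled test carries no cluster degrees of freedom, and the dropout step is not run within imputation

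*SAP*

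**What the plan says.** SAP 7.2.3 handles missing monthly reports in two steps, then analyses and pools.

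- **Step 1, intermittent gaps.** Run by treatment arm and written to `outimp1`: "In this step, this MI procedure produces 30 imputed datasets by filling in the missing values from intermittent missingness".
- **Step 2, dropouts.** The call is "PROC MI DATA=outimp1 nimpute=1 OUT=outimp2 SEED = 100623". It has CLASS, VAR, MONOTONE and MNAR statements and draws on the EUC arm only. It has no BY statement.
- **Analysis.** The text says the model is fitted separately to each of the 30 completed datasets, and the GLIMMIX call has `BY _imputation_`. Its MODEL statement gives the distribution and link but no `ddfm=`, and the PROC line has no `method=quad`.
- **Pooling.** The call is "PROC MIANALYZE PARMS=mixparms", with no `EDF=` option. The text explains that "Between-imputation variance reflects the extra variance due to the missing data".

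The primary model in SAP 7.2.2 differs from the model fitted to the imputed data. It uses Gaussian quadrature and "MODEL daysin180 = treat site baseline / solution DIST=negbin LINK=log ddfm=bw", that is, between-within degrees of freedom. SAP 9.0 sets a two-sided 5% test for the primary outcome. No text in either document gives the degrees of freedom for the pooled test or says that step 2 runs within imputation. Protocol 14.10 leaves the imputation details to the SAP.

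**The concern.** Treatment is assigned by PCP or PCP team, so the evidence on the treatment effect comes from about 60 clusters. `ddfm=bw` in 7.2.2 looks like a deliberate allowance for that. Without it in the imputed-data model, and without `EDF=` at pooling, the allowance does not reach the one confirmatory test. The pooled reference distribution then depends only on the number of imputations and the missing information, and is close to normal.

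In step 2, `outimp1` holds 30 stacked copies of the trial. Without `BY _Imputation_`, one control-arm regression is fitted to all the stacked rows, and one parameter draw serves all 30 copies. Uncertainty in the regression parameters should vary from one imputation to the next and so enter the between-imputation variance; here it does not. If the procedure also rewrites its index variable, the next step has no valid grouping.

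The post hoc zero-inflated models in SAP 14.1 use the same multiply imputed datasets, so a fault in step 2 carries into them.

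**Working it through.** **Inputs.** m = 30 imputations (SAP 7.2.3). About 60 PCPs with about 5 patients each (Protocol 2.1.2), with 50 PCPs × 4 as the worst case (SAP 10.0). Five sites (SAP 7.2.2). Up to 20% of participants missing the primary endpoint, dropout and nonresponse together (SAP 7.2.3). PCP variance 0.15 and individual variance 0.25 (SAP 10.0).

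**Assumed.** Complete-data degrees of freedom ν₀ = clusters − 6 (intercept, treatment, four site terms), inferred from `ddfm=bw`. This gives 54 for 60 clusters and 44 for 50. The alternative is residual degrees of freedom, patients − clusters − 6: 300 − 60 − 6 = 234, or 200 − 50 − 6 = 144. The fraction of missing information λ is taken from 0.05 to 0.20. The simulations below gave about 0.05 to 0.11, so 0.20 is an upper bound.

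**Check against the plan's own figure.** The SAP gives power of 0.97 and 0.93 for 60 PCPs × 5 patients, Scenarios 1 and 2. Simulation with the stated variances, 20% dropout and a fresh individual intercept in each 90-day interval (400 runs) gave 0.970 and 0.933. The other three conditions agreed within 2 points. With a single individual intercept shared across intervals, 60 × 8 still agrees. However, 60 × 5 Scenario 1 falls to 0.940, and 50 × 4 Scenario 2 falls to 0.82 against a stated 0.89.

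**Degrees of freedom.**

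- Without `EDF=`: ν_m = (m − 1)/λ². At λ = 0.05 this is 29/0.0025 = 11,600; at λ = 0.20 it is 29/0.04 = 725.
- With `EDF=` (Barnard-Rubin): ν_obs = [(ν₀ + 1)/(ν₀ + 3)] ν₀ (1 − λ), and ν = 1/(1/ν_m + 1/ν_obs).
- Example, 60 clusters, λ = 0.05: ν_obs = (55/57) × 54 × 0.95 = 49.5, so ν = 49.3. The critical value is 2.009 against 1.960, and 1 − 1.960/2.009 = 2.4%.

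| ν₀ | λ | ν | critical value with EDF | without EDF | printed interval narrower by | size of nominal 5% test |
|---|---|---|---|---|---|---|
| 54 | 0.05 | 49.3 | 2.009 | 1.960 | 2.4% | 5.6% |
| 54 | 0.20 | 39.4 | 2.022 | 1.963 | 2.9% | 5.7% |
| 44 | 0.05 | 39.9 | 2.021 | 1.960 | 3.0% | 5.7% |
| 44 | 0.20 | 32.2 | 2.036 | 1.963 | 3.6% | 5.8% |
| 234 | 0.05 to 0.20 | 216 to 148 | 1.971 to 1.976 | 1.960 to 1.963 | 0.55% to 0.65% | 5.1% to 5.2% |
| 144 | 0.05 to 0.20 | 133 to 98 | 1.978 to 1.984 | 1.960 to 1.963 | 0.9% to 1.1% | 5.2% |

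**Missing BY.** Control-based monotone regression imputation was simulated for 60 × 5 with 20% dropout, and the negative binomial random-intercept model was fitted to each completed dataset. A fresh parameter draw per dataset was compared with one draw from the 30-fold stack, with the index assumed kept (45 replicates).

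- Dropout spread over months 1 to 6: SE ratio (without BY to with BY) 0.9997, Monte Carlo SE 0.002.
- All dropouts gone before month 1: ratio 0.9957, Monte Carlo SE 0.004.

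The reduction is therefore about 0% to 0.5%, not clearly distinguishable from zero. Noisier 12-replicate runs over other settings gave changes from a 0.6% increase to a 1.4% reduction. With both omissions, the 45-replicate intervals were 2.5% and 3.0% narrower than with BY and `EDF=`, nearly all of it from the degrees of freedom.

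**The case against.** The strongest reply is that this is template code under sound prose. Step 2 writes `outimp2`, but the model reads `outmi`. The estimates are saved as `GPARMS`, but pooling reads `mixparms`. Pooling names a class variable, `visno`, that is defined nowhere, and the bounds list has eight entries for nine variables. Code in that state would not run as printed, so no actual interval can be called too narrow. The text does call for separate analysis of 30 completed datasets. It also promises no particular degrees of freedom for the pooled test, and the protocol's example code names no such method, so 54 is an inference. Finally, the SAP describes its control-based imputation as conservative.

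Much of this stands. The percentages describe a literal reading of the code under stated assumptions, not a result of the trial, and they shrink to about 1% or less with residual degrees of freedom. The prose does not close the gap, though. An analyst who repairs the block must choose the pooled degrees of freedom, the estimation method and the grouping in step 2. Each choice affects the primary p-value, and none is recorded.

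A reader might infer that the missing BY statement causes the 2% to 3% narrowing. The calculations do not support this: at planned missingness that omission is worth about 0.5% or less if the index is kept.

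**Conclusion.** The point holds as a mismatch between the printed primary procedure, its own description and the 7.2.2 model.

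- **Degrees of freedom.** If between-within degrees of freedom are intended, the printed interval is about 2.4% to 2.9% too narrow with 60 clusters and 3.0% to 3.6% with 50. The nominal 5% test is about 5.6% to 5.7% with 60 clusters and 5.7% to 5.8% with 50. With residual degrees of freedom the narrowing is about 0.5% to 1.1%. All of this assumes missing information of 5% to 20%.
- **Missing BY.** The effect on the standard error is about 0% to 0.5% if the imputation index keeps its values 1 to 30. If step 2 overwrites it, the by-imputation analysis and pooling are invalid and the percentages above do not apply. The documents do not settle which.

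A reader might also infer that the confirmatory test has a materially inflated error rate. The documents do not support that: the excess is under one percentage point before the conservatism of control-based imputation, and the net rate may stay near 5%. The reason to act is that this is the only primary test and the correction is cheap.

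**What to change.** - Sort `outimp1` by `_Imputation_` (step 1 runs by treatment arm) and add `BY _Imputation_;` to the second PROC MI, keeping `nimpute=1`.
- Carry `method=quad` and `ddfm=bw` from 7.2.2 into the GLIMMIX call on the imputed data.
- Add `EDF=` to PROC MIANALYZE, set to the between-cluster degrees of freedom (PCP clusters with patients, minus the intercept, treatment and site parameters). State that rule in the text of 7.2.3.
- Align the dataset names (`outimp2`/`outmi`, `GPARMS`/`mixparms`) and replace or remove `visno`. Check the bounds list against the variable list at the same time.

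The cost is a few lines of code and one sentence, with no new data. The downside is a slightly wider interval. If the analysis has already been run, report which version of these steps was used.

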7.3 Sensitivity Analyses of the Primary Outcome Measure

Mechanisms of missingness cannot be determined from observed data alone, therefore sensitivity analyses will be done to compare different assumptions of missingness in order to assess the robustness of the conclusions from the primary outcome analysis with multiple imputation. The following sensitivity analyses of the primary outcome will be conducted:

1. Conducting a complete-case analysis. Here the complete case population (a subset of the ITT population) will be fit with the same model as specified in Section 7.2.2. The complete case population is the set of the patient participants with no missing values for the primary outcome in Months 1-6 and baseline level of days of risky opioid use. Note that the variables of treatment, site, and PCP cluster will have no missing values.
2. Conducting multiple imputation by assuming the missing data mechanism is MAR for both the intermittent missingness pattern and the dropout scenario under the assumption that the values of missingness remain the trend of the observed values regardless of the exposure in the study environment.

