14.10 Missing Data and Dropouts

The primary outcome, number of days of risky opioid use within the first 180 days since baseline, is measured by repeated monthly assessments. For each monthly assessment, participants will record the number of days of risky use within the previous 30 days. We consider two types of missing data for this outcome:

- *Missingness due to dropout*: participants may withdraw early from the study and miss all subsequent monthly measurements.
- *Intermittent missingness*: participants may miss one or more monthly surveys while remaining enrolled in the study.

It is anticipated that up to 20% of participants may be missing data for the primary endpoint due to dropout and/or nonresponse. It is possible that participants who drop out will have higher use after their dropout date than those who remain in the study. For example, it is possible that days of use after the withdrawal timepoint for dropouts in the treatment arm may more closely resemble that of controls than that of other treated participants. In this case it is possible that a complete case analysis could overestimate the treatment effect if there is a high level of missing data (and if control dropouts do not have an analogous increase). Multiple imputation will be performed for the primary analysis to account for missingness of the primary outcome variable. A repeated measures model with treatment by time interactions will be created for the imputation in order to take full advantage of information from partial reports by participants with intermittent missingness. Information on days of risky use assessed by TLFB will be included in the imputation model. Further details of the imputation models will be specified in the SAP. If multiple imputation is performed, a complete-case analysis will be performed as a secondary analysis. In either case, sensitivity analyses will be performed to assess robustness of the treatment effect estimate to different patterns of responses for the missing values.

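### No planned analysis of the primary outcome tests heavier use after dropout than the EUC-based imputation predicts

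*SAP*

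**What the plan says.** SAP 7.2.3 treats intermittent gaps as missing at random and dropout as missing not at random. For dropout it states: "It is assumed that patient participants who drop out will have higher use after their dropout date than those who remain in the study". The same sentence then explains what is meant, namely that use after withdrawal for "dropouts in the treatment arm may more closely resemble that of controls than that of other treated patient participants".

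The dropout step is control-based: "only the observed values in EUC group are used to derive the posterior distribution of the parameters", and those parameters are used to impute both arms. The code is an MNAR statement, "MNAR model(daysinmon1-daysinmon6/ modelobs", pointing to the EUC arm. It contains no shift or scale adjustment. Site, baseline use and earlier months are in the variable list, so each dropout is imputed conditional on their own history. The SAP comments: "This approach is conservative as it tends to reduce the difference between STOP group and EUC group".

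SAP 7.3 lists two sensitivity analyses: complete case, and "Conducting multiple imputation by assuming the missing data mechanism is MAR for both the intermittent missingness pattern and the dropout scenario". Protocol 14.10 plans the complete-case analysis as a secondary analysis, warns that it could overestimate the effect, and separately promises that "sensitivity analyses will be performed to assess robustness of the treatment effect estimate to different patterns of responses for the missing values".

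No other analysis goes further. The covariate-adjusted and per-protocol analyses (SAP 7.4) use no imputation, the subgroup table shells state that missing values are not imputed, and the zero-inflated models (SAP 14.1) reuse the same imputed datasets.

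**The concern.** Sensitivity analyses are most useful on the side that could overturn a positive result. Here the primary is the least favourable to STOP of the three under the planning means, and both checks sit on the other side of it. Agreement among them would say nothing about what happens if people who leave go on to use more than an EUC participant with the same history.

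The sponsor already recognises one route to STOP-specific disengagement. Exploratory Objective 1 reports that, in an earlier trial of one component, intervention patients whose opioids were stopped were less likely to follow up with their PCP. That concerns clinic follow-up rather than survey dropout, but it makes an arm-specific departure worth testing.

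**Working it through.** **Inputs from the documents.** 180-day means of 40 (EUC) and 28 (STOP), Scenario 1; PCP and individual intercept variances of 0.15 and 0.25 (SAP 10). Up to 20% missing the primary endpoint (SAP 7.2.3), applied here as dropout in each arm.

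**Assumed, not in the documents.** Last observed month spread evenly over 0 to 5 (on average 2.5 months observed, 3.5 missing); dropout unrelated to earlier use; the multipliers; the unequal dropout rates.

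**Step 1: reproduce the plan's figures.** With the intercepts on the logit scale, the middle half of EUC PCP means runs from 17.2 to 25.2 (SAP: 17 to 25). Power for 60 PCPs with 5 patients each, Scenario 1, comes to 0.96 (SAP: 0.97) if the individual intercept is redrawn for each 90-day interval, and 0.934 if it is held fixed. The point does not rest on power; this only checks the inputs. The intercepts raise both means: averaging 180 × expit(logit(m/90) + N(0, 0.40)) gives 43.1 for m = 20 and 31.1 for m = 14. The ratio without dropout is therefore 31.1/43.1 = 0.72, not 28/40 = 0.70.

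**Step 2: hand calculation on the nominal means.** For an arm with mean M, dropout d, and later use k times the EUC monthly level (40/6 = 6.67):

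mean = (1 − d)M + d(2.5M/6 + 3.5 × 6.67k)

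With d = 0.20:

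| Dropouts' later use | EUC | STOP | Ratio |
|---|---|---|---|
| No departure | 40 | 28 | 0.700 |
| STOP at EUC level | 40 | 22.4 + 0.2(11.67 + 23.33) = 29.40 | 0.735 |
| STOP at 1.25 times | 40 | 22.4 + 0.2(11.67 + 29.17) = 30.57 | 0.764 |
| STOP at 1.5 times | 40 | 22.4 + 0.2(11.67 + 35.00) = 31.73 | 0.793 |
| Both at 1.5 times | 32 + 0.2(16.67 + 35.00) = 42.33 | 31.73 | 0.750 |
| EUC at 1.5, STOP at 1.0 | 42.33 | 29.40 | 0.694 |

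**Step 3: simulation of the planned methods.** Monthly Binomial(30) counts, 60,000 per arm. Dropouts are imputed by sequential bounded regression on earlier months, using EUC parameters (primary) or own-arm parameters (MAR). Ratios are STOP/EUC; dropout is 20% per arm unless stated.

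| Dropouts' later use | True | Complete case | MAR | Primary |
|---|---|---|---|---|
| Own-arm path | 0.726 | 0.725 | 0.728 | 0.747 |
| STOP at control level | 0.760 | 0.725 | 0.729 | 0.748 |
| STOP at 1.25 times | 0.789 | 0.725 | 0.729 | 0.748 |
| STOP at 1.5 times | 0.819 | 0.725 | 0.729 | 0.748 |
| Both at 1.25 times | 0.762 | 0.725 | 0.726 | 0.745 |
| Both at 1.5 times | 0.769 | 0.725 | 0.726 | 0.745 |
| EUC at 1.5, STOP at 1.0 | 0.714 | 0.725 | 0.726 | 0.745 |
| Both at 1.5; dropout 25% STOP, 15% EUC | 0.801 | 0.725 | 0.727 | 0.751 |
| Both at 1.5; dropout 15% STOP, 25% EUC | 0.737 | 0.725 | 0.725 | 0.739 |

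The simulated level of 0.725 is about 0.005 above the 0.72 from Step 1; gaps between columns are steadier than levels. The hand ratios are about 0.02 to 0.03 lower because they start from 0.70, but they keep the same order.

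Two features stand out. In every row the primary is less favourable to STOP than MAR or complete case. With STOP dropouts exactly at control level it still falls slightly short (0.748 against 0.760), because it conditions on their lower STOP history. If all dropout precedes month 1 there is no such history: the primary gives 0.781 against a true 0.782, but the truth is 0.832 or 0.882 at 1.25 or 1.5 times.

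**The case against.** The strongest reply is that the SAP does what it says. Reading only the opening clause, that "patient participants who drop out will have higher use after their dropout date than those who remain in the study", one might infer that the primary imputation ignores the SAP's own assumption, or that use above EUC level is part of it. The documents do not support that. The sentence goes on to define the assumption as STOP dropouts resembling controls, and the control-based step largely implements this. Protocol 14.10 offers the same example and adds a condition that control dropouts show no matching rise.

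A reader might also infer that all planned analyses must overstate benefit. That fails too. The direction depends on which arm's dropouts use more: the primary understates benefit when EUC dropouts are the heavier users, and is about right with both at 1.5 times and more dropout in EUC. Nor are imputed STOP values capped at the EUC mean, since a patient already using heavily is predicted high. Complete case is not always the more favourable analysis either; if heavier EUC users leave, it could move the other way.

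The remaining replies are fair in part. The conservatism claim carries its reason in the same sentence and holds relative to MAR. Missing-data patterns will be tabulated by arm, so unequal dropout will be visible. Effects can be small: with dropout after month 3, 20% per arm and doubled use in both arms, the hand ratio is (22.4 + 0.2 × 54)/(32 + 0.2 × 60) = 33.2/44 = 0.75, against 29.2/40 = 0.73 with later use at EUC level.

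What stands is the gap. Tabulating dropout does not show its effect on the estimate, and nothing planned varies post-dropout use beyond the EUC-based prediction.

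**Conclusion.** The concern holds as a gap in the sensitivity analyses, not as a contradiction within the SAP. Under the planning means, the two analyses in 7.3 lie on the STOP-favouring side of the primary, and the less favourable side promised in general terms by Protocol 14.10 is not examined.

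With 20% dropout per arm and evenly spread timing, the primary is more favourable than the truth by about 0.04 (0.789 − 0.748) or 0.07 (0.819 − 0.748) when STOP dropouts use 1.25 or 1.5 times the control level, and by about 0.02 (0.769 − 0.745) when both arms' dropouts use 1.5 times. In the opposite case it is less favourable by about 0.03 (0.745 − 0.714). All these ratios stay below 1, so the departure would matter mainly if the upper confidence limit were close to 1. The multipliers, timing and unequal rates are illustrative assumptions, not predictions.

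**What to change.** Add to SAP 7.3 a delta-adjusted or tipping-point analysis on the existing 30 imputed datasets:

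- Multiply only the months imputed in the dropout step by, for example, 1.25, 1.5 and 2.0, capped at 30 days per month. Then re-sum to 180 days, refit the primary model and pool.
- Do this in STOP only, in EUC only, and in both arms. The EUC-only run is needed because the primary can err in either direction.
- Report the multiplier at which the conclusion changes.
- If the primary analysis has already been run, label this post hoc, as SAP 14.1 does for the zero-inflated models.

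In SAP 7.2.3, qualify the description of the approach: conservative relative to MAR, provided dropouts do no worse than the EUC-based prediction.

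The cost is a loop over existing datasets and one more table. No new data or imputation model is needed.
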